Appendix A

This report provides information on detailed technical methods for handling of issues for the analysis of 6-month client data as well as 12-month and 3 years follow-ups.

Table of Contents		Page
A1	Analytic Sample	A-2
A2	Weighting	A-3
A3	Multiple Imputation	A-4
A4	Analyses	A-6
A5	References for Appendix	A-10

A1. Analytic Sample

Enrollment

The study settings were South Los Angeles and Hollywood-Metro. Participant sampling (program and client recruitment) and randomization are described in greater detail in prior publications. Within enrolled programs, clients were screened for eligibility in waiting rooms (consecutive selection) or events (random selection) between March 2010 to November 2010 by community members blinded to intervention condition and supervised by RAND. Staff approached 4,645 adults (age \geq 18) over 2-3 days per program; 4440 (96%) agreed to screening. Study eligibility was limited to clients providing contact information and depressed based on a score of 10 or greater on a modified 8-item Patient Health Questionnaire (PHQ-8) (3). Of 4,440 screened, 1,322 (30%) were eligible and 1246 (94%) consented. In our previous publications,(1-3) we created enrollment weights based on propensity weighting adjustment, by fitting logistic regression models to predict the enrollment among those eligible. The reciprocal of the predicted response probability was used as the enrollment weight for each participant. See Supplementary Materials in publications. ¹⁻⁵

Telephone survey

Baseline survey. Between April 27, 2010-January 2, 2011, we approached 1,246 consented clients for baseline telephone survey conducted by survey staff blinded to intervention condition and 981 clients (79% of 1246 consented, RS: 492, CEP: 489) completed the baseline, 36 refused (RS: 17, CEP: 19), 227 were unable to contact (RS: 96, CEP: 131), and 2 deceased (RS: 1, CEP: 1).

6 month follow-up survey. Between November 2, 2010 and August 11, 2011, we approached 1093 participants (RS: 540, CEP: 553) for 6-month follow-up telephone survey; 153 enrolled participants were excluded from the contact list because their baseline survey response status was in one of following categories: final refusal, ill or incarceration, unable to contact, or deceased. Of 1093 attempted for 6-month follow-up, N=759 (69% of attempted, RS: 380, CEP: 359) completed the survey, 12 refused (RS: 3, CEP: 9), 321 were unable to contact (RS: 157, CEP: 164), and 3 deceased (RS: 1, CEP: 2).

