For all study components (including supplement components discussed below), we convened working groups co-chaired by academic and community members to review analysis plans, data output and discuss findings.

Analyses for 6-month outcome: We conducted intent-to-treat, comparative-effectiveness analyses with intervention status as the independent variable, using logistic regression for dichotomous measures and Poisson regression models for count variables. Covariates were selected to account for known associations of sociodemographic and clinical status indicators with primary outcome measures. We adjusted for baseline status of dependent variables and covariates (age, sex, ≥ 3 chronic general medical conditions from a list of 18, education, race/ethnicity, family income < federal poverty level, 12-month alcohol abuse or use of illicit drugs at baseline, 12-month depressive disorder at baseline, and community). All analyses were conducted using SUDAAN Version 10.0 (<http://www.rti.org/sudaan/>) and accounted for clustering (clients within programs), weighting, and multiple imputations. Significance of comparisons by intervention status was based on regression coefficients. Results of logistic regression models are presented as odds ratios (OR) and Poisson models as rate ratios (RR) with 95 % confidence intervals. We illustrate results for intervention groups adjusted for covariates using standardized predictions generated from fitted regression models.¹⁴ We present Cohen's effect size index h , defined for dichotomous variables,¹⁵ where $h=0.20$ is small, $h=0.50$ is medium and $h=0.80$ is large. We supplement adjusted models with unadjusted raw data to assess

robustness. We applied a Bonferroni adjustment considering two primary outcomes (Poor mental health qualify of life $MCS-12 \leq 40$, and at least mild depression $PHQ-9 \geq 10$) and compared the proportion of results across outcomes favoring one intervention to an assumed null-hypothesis of 0.5.

Analyses for 12-month outcome: We conducted intent-to-treat analyses of repeated measures including all participants with available data at baseline, 6-, or 12-months by using SAS software version 9.2 (SAS Institute). We used a model-based approach with unweighted data. Initial explorations of 3-level, random-effects logistic models using SAS PROC GLIMMIX for binary outcomes yielded unstable estimates for program-specific random effects.^{16, 17}

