We analyzed dichotomous and count outcomes by using a generalized estimating equation (GEE) framework.¹⁸ Specifically, we fitted logistic regression models for binary outcomes and Poisson models for count data using SAS PROC GENMOD, specifying exchangeable correlation at the program level, with regression adjustment for baseline covariates (age, sex, ≥ 3 chronic conditions, education, race/ethnicity, family poverty, alcohol abuse or use of illicit drugs in the past 12 months, depressive disorder in the past 12 months, and community). We then developed a contrast involving a linear combination of coefficients to test intervention effects at each end point (baseline, 6 months, and 12 months) and tested differences between intervention groups in change from baseline to 6 and 12 months.

The results of analyses of binary outcomes are presented as odds ratios, and the results of Poisson regression analyses of count data are presented as rate ratios. We treated time as a continuous variable and examined the fixed effects for time and intervention, and their interactions. We included quadratic terms (squared effect of time and its interaction with the intervention) which allowed insight into whether changes are greater from baseline to 6 months or subsequent months.

In analyzing continuously scaled MCS-12 as the dependent variable, we used a 3-level, mixed-effect regression model by using SAS PROC MIXED. We accounted for the multilevel data structure with clients nested within pro-grams and repeated measurements nested within clients. To account for the intraclass correlation expected in the data, we specified random effects at the program level and an autoregressive covariance structure within clients to account for within-client correlation over time.

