We conducted a longitudinal sensitivity analysis using all waves of data (baseline, 6-months, 12-months, 3-years) without response weights, adjusting for baseline covariates as in the primary analysis. We specified a spline model, with a linear segment between baseline and the first follow-up for initial improvement and another linear segment for the subsequent follow-ups; the two linear segments were specified to join at the first follow-up. In analyzing continuously scaled PCS-12 as the dependent variable, we used a 3-level, mixed-effects regression model by using SAS PROC MIXED. To account for the intraclass correlation due to the multilevel structure, we specified random effects at the program level and a spatial power covariance

structure at the client level to account for unequal spacing of waves. Initial explorations of 3-level, random-effects logistic models using SAS PROC GLIMMIX for binary outcomes yielded unstable estimates for program-specific random effects. We utilized a generalized estimating equation (GEE) framework with logistic regression models for binary outcomes and Poisson models for counts using SAS PROC GENMOD, specifying exchangeable correlation at the program level. From the estimated spline models, we developed a contrast involving a linear combination of coefficients to test intervention effects at each end point (baseline, 6-months, 12-months, and 3-years) and tested differences between intervention groups in change from baseline to 6 months, 12 months, and 3 years.

Exploratory analyses. The CPIC study had 2 primary outcomes: poor MHRQL (12-item mental health composite score, MCS-12 \leq 40), and depressive symptoms (PHQ-8 \geq 10 or PHQ-2 $<$ 3 for 4-year follow-up); and a community-prioritized outcome of mental wellness (a response of at least “a good bit of the time” in the previous 4 weeks to feeling calm or peaceful, having energy, or being happy), based on community input matched to the 36-item short-form health survey quality-of-life items. We developed 2 indicators: “clinical remission” (PHQ-8 $<$ 10 or PHQ-2 $<$ 3) and, with stakeholder input, “community-defined remission” (PHQ-8 $<$ 10 or PHQ-2 $<$ 3 or MCS-12 $>$ 40 or any mental wellness). We also used a count of survey periods in remission from baseline up to 3-year follow-up. Intervention status was the client’s program assignment at enrollment to CEP or RS.

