For time (survey period) to first remission, we used Cox proportional hazard models for the full sample with any survey data (n = 1018), limited to those at risk for subsequent clinical (n = 995) and community-defined (n = 408) remission at baseline. We used linear regression for number of periods in remission during the course of 3 years for the full sample (n = 1018). We developed models including intervention status, adding social determinants, then depression treatment.⁵

Analyses for 4-year outcome:

We conducted intent-to-treat analyses with intervention status as the main independent variable, using logistic regression for probability of remission (clinical, community-defined) for the sample with 4-year data (n = 298). We conducted analyses parallel to the 3-year analyses noted previously, using the same covariates plus base-line measure of the outcome and the 1 baseline item differing by intervention status among 4-year completers.⁵

A5. References

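### The depression primary (PHQ of 10 or more) repeats the entry cut-off, so its baseline status is nearly constant: adjusting for it adds almost nothing, and its change-from-baseline contrasts are too imprecise to inform

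*Combined protocol and SAP*

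**What the plan says.** **Entry.** Appendix A1 (Enrollment) limits eligibility to clients who gave contact information and were "depressed based on a score of 10 or greater on a modified 8-item Patient Health Questionnaire (PHQ-8").

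**Outcome.** Appendix A4 dichotomises the depression primary at the same value: a PHQ-9 of 10 or more at 6 months, and a PHQ-8 of 10 or more in the 3-year work (also Section 6, Measures).

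**Adjustment.** For the 6-month logistic model A4 states "We adjusted for baseline status of dependent variables and covariates". The listed covariates include 12-month depressive disorder but no PHQ score. The 3-year endpoint analysis refers back to this strategy, and a 12-month endpoint analysis also controls for baseline.

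**Change tests.** The 12-month GEE treats baseline as an outcome wave. Besides arm contrasts at each time point, the authors "tested differences between intervention groups in change from baseline to 6 and 12 months". The 3-year longitudinal sensitivity analysis likewise "tested differences between intervention groups in change from baseline to 6 months, 12 months, and 3 years". Neither passage exempts any outcome.

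**Baseline distribution.** The exploratory section of A4 defines clinical remission as a PHQ-8 below 10 (PHQ-2 at 4 years). It gives the time-to-remission samples, out of 1,018, as "limited to those at risk for subsequent clinical (n = 995) and community-defined (n = 408) remission at baseline".

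**The concern.** An own-baseline covariate helps when it separates clients by starting level. Here the entry rule has already placed nearly everyone in one category. If the term is the yes/no status, a client who entered with a PHQ-8 of 10 and one who entered with 24 get the same value on it. Chance differences in severity between arms are then removed only as far as the other covariates capture them.

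The change contrasts raise a second problem. On the log-odds scale a proportion close to 1 is estimated poorly, and a change contrast carries that imprecision into the result. A null change contrast could be read as evidence that CEP did not affect depression, when it mostly reflects how few clients were below the cut-off at baseline.

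**Working it through.** **1. The plan's own power figure.** Table 4, final row: N = 780, 80% power, two-sided 0.05, ICC 0.00-0.02. A two-sample t calculation gives 0.2009 (9.98 percentage points) at ICC 0. At ICC 0.02 with 80 programs, m = 780/80 = 9.75 and VIF = 1 + 8.75 × 0.02 = 1.175, which gives 0.2202 (10.92 points). Both match Table 4 with no credit for baseline adjustment, so this point does not touch the planned sample size.

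**2. Baseline status.** 995/1,018 = 97.7% positive. 1,018 − 995 = 23 negative (2.3%). Baseline log-odds = ln(995/23) = 3.77.

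**3. What the yes/no term can explain.** With baseline-negative share q = 0.0226 and follow-up positive share p, the largest possible squared correlation between the two indicators is [q/(1−q)] × [p/(1−p)]. The documents do not give p, so I assume 30-70%:

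| p at 6 months | largest share of variance |
|---|---|
| 30% | 0.0231 × 0.429 = 1.0% |
| 50% | 0.0231 × 1 = 2.3% |
| 70% | 0.0231 × 2.333 = 5.4% |

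**4. Precision of the change contrast.** Assumptions: 509 clients per arm at baseline, the 23 negatives split 11.5 and 11.5, about 380 per arm at 6 months (759 stated completers), half positive at 6 months, no clustering or weights.

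- Baseline log odds ratio: variance = 2 × (1/11.5 + 1/497.5) = 0.178; SE = 0.42.
- 6-month log odds ratio: variance = 2/(380 × 0.25) = 0.0211; SE = 0.145.
- Change, waves independent: variance = 0.178 + 0.0211 = 0.199; SE = 0.446. With a correlation of 0.2 between the two estimates, SE = 0.418.
- Share of variance from baseline: 0.178/0.199 = 89% (88% at 30% or 70% positive).
- Power: an effect with 80% power at 6 months sits at z = 2.80. As a change contrast it sits at 2.80 × 0.145/0.446 = 0.91, for power of about 15% (16% with the correlation of 0.2).
- Detectable odds ratio at 80% power: exp(2.80 × 0.145) = 1.50 for the endpoint; exp(2.80 × 0.446) = 3.49 for the change.

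The time model does not rescue this. A quadratic in time crossed with arm fits three waves exactly, and the 3-year spline still estimates a free baseline level in each arm.

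**5. Sensitivity to the split.** If the 23 fall 8 and 15, the baseline odds ratio is (501/8)/(494/15) = 1.90 by chance alone, and this passes straight into the change estimate. A 5 and 18 split raises the SE of the change to 0.53.

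**6. Value of the continuous score.** This was simulated for 780 clients with a latent baseline truncated to its top 30% (1,322 of 4,440 screened were eligible). The score was worth about 6% in effective sample size at an assumed latent correlation of 0.5 and about 8% at 0.6, before any other covariate. The power section assumes an inter-temporal correlation of 0.50 in general, not for the PHQ in particular.

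**The case against.** **The baseline term may be the score.** The text does not say whether the term is the indicator or the score, or whether it comes from the screener or the baseline interview; the Table 3 footnote allows either. If the score was used, the adjustment point largely disappears. That possibility stands. However, baseline status of a yes/no outcome most naturally means the yes/no value. No PHQ score appears among the outcome-model covariates, although Appendix A3 uses one in the imputation models. The change-contrast point holds either way, because the GEE outcome is binary.

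**The 23 is inferred.** It comes from an exploratory time-to-remission sample, not from the primary model, and only 981 clients completed the baseline interview. This is fair. If baseline means the screener itself, near-constancy follows from the entry rule and the problem is worse.

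**Severity is not uncontrolled.** A reader might infer that it is. The documents do not support that, since 12-month depressive disorder, taken from the diagnostic interview, is in the models. It is coarse, but it does part of the work and would reduce the 6-8% gain.

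**The conclusions do not hang on the change tests.** The 12-month model also gives arm contrasts at 6 and 12 months, A4 adds a 12-month endpoint analysis, and the main 3-year analysis is an endpoint analysis. The 3-year change tests sit in a sensitivity analysis. All of this stands and limits the weight of the point.

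**Conclusion.** The point holds for the PHQ outcome cut at 10, with limited reach. Read as the dichotomy, its own-baseline term explains at most about 1-5% of outcome variance (assuming 30-70% positive at 6 months), so it adds almost nothing. Its change-from-baseline contrasts have an SE of about 0.42-0.45 against 0.145 for the 6-month comparison, and about 15% power where the endpoint has 80%. These figures rest on an even split of the 23, half positive at 6 months and no clustering. A null change contrast says nothing useful about CEP.

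Three stronger readings are not supported:

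- **That the depression result is invalid or the trial underpowered.** The endpoint comparisons at 6, 12 and 36 months are randomised comparisons, and Table 4 takes no credit for baseline adjustment.
- **That the change tests use only 23 clients.** The follow-up half uses all responders; the 23 dominate the variance (about 88-90%) on the log-odds scale.
- **That the problem extends to other outcomes.** MCS-12 was not an entry criterion. Only 408 of 1,018 were at risk of community-defined remission at baseline. The entry rule did not fix the PHQ-2 used at 4 years.

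**What to change.** For the PHQ outcome cut at 10 only:

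1. State which baseline PHQ variable enters the models and from which survey. Use the continuous screening PHQ-8 total as the baseline covariate in the 6-month, 12-month endpoint and 3-year endpoint models.
2. In the 12-month GEE and the 3-year longitudinal sensitivity model, remove the baseline wave from the outcome vector, include the screening PHQ-8 total as a covariate, rely on the arm contrasts at 6, 12 and 36 months, and drop the change-from-baseline contrasts.

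The cost is SAP wording and a re-run on a variable already collected at screening. The PHQ longitudinal model will differ slightly from the MCS-12 model. Appendix A describes analyses already done, so where results have been reported the re-analysis should be labelled post hoc and shown beside them.

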Assumptions of normality will also be evaluated. For example, we will explore various transformations (e.g., log and square root) for life event variables due to the often skewed distribution of event counts. Smearing estimates will be used, if necessary, for retransformation, applying separate factors for each intervention group to ensure consistent estimates.^{161, 162} In general, we leave open the possibility of transforming variables with non-normal distributions. In certain cases, the outcome of interest will have a very skewed distribution, either because there will be many zeros (e.g. sick days) and/or because the distribution of observed values has a very long tail (e.g. services utilization). In such cases, we will draw upon statistical models developed for handling these type of data, in particular a two-part model to separately handle zero values and a skewed distribution among non-zeros¹⁶¹ Tobit-type sample selection models¹⁶³; split-sample techniques to distinguish between different functional forms and to avoid overfitting¹⁶¹; and dynamic models, such as episodes of care analytic models, duration analysis, and count models.^{164, 165}

Multiple Comparisons: We will address multiple comparisons by comparing the proportion of results favoring one intervention to an assumed null-hypothesis value of 0.5. We will consider but will not rely solely on Bonferroni adjustments and related methods that incorporate bounds on the probability of a single false finding of significance. We will also consider the false discovery rate (FDR)¹⁶⁶, a framework that offers more sensitive tests of significance when large numbers of tests are carried out by comparing observed significance findings with expected order statistics from a uniform distribution.

Hypotheses and Analysis Plans for Aim 2: *To examine the effects on client access to care, quality of care, and depression-related outcomes.*

Hypotheses: We hypothesize that the community-engagement approach will lead to greater improvement over 6-12months in client's access to care, quality of care, and health outcomes than the technical assistance condition. In underserved communities, greater participation in planning, which community engagement instills, is anticipated to improve uptake of health interventions.³⁴ Further, the community-engagement intervention utilizes many principles of social-science theory that support behavior change such as practice and skill development^{104, 124,}

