Overview: The primary goal in this group-level randomized trial is to estimate the difference in effects on outcomes, between intervention arms (e.g., CE condition vs. low-intensity control). To test our main hypotheses (that CEP would be more effective than RS in improving client health outcomes and addressing community priorities for housing and employment, while likely increasing services utilization), we will conduct intent-to-treat, comparative effectiveness analyses using intervention status as the independent variable. We will estimate logistic regression models for indicator variables and loglinear models for counts. Consistent with recommendations for group-level trials, (8) main models will incorporate adjustment for baseline status of dependent variables and covariates: age, sex, ≥ 3 chronic conditions, education, race/ethnicity, family poverty, 12-month alcohol abuse or illicit drug use, 12-month depressive disorder, and community. We will weight data for clients with baseline or six-month data to characteristics of eligible clients. For missing data, we will use item-level ^{155, 168} and wave-level ¹⁶⁹ imputation. Estimates and p-values are calculated using SUDAAN (<http://www.rti.org/sudaan/>) taking into account clustering within programs and weighting. We supplement findings from adjusted models with results from raw data to assess robustness. We will use two-sided tests with $p < .05$ for statistical significance.

We will also explore as an alternative approach multi-level models (also known as hierarchical models or random coefficient models) to account for the multilevel data structure with clients nested within units (agencies or relatively autonomous subdivisions thereof), and repeated measurements nested within clients.¹⁷⁰⁻¹⁷³ For this approach, we will apply two-level models for the cross-sectional data with clients nested within units; and three-level models for the longitudinal data with repeated measurements nested within clients and clients nested within units. To perform multilevel analyses, we will use special software such as the MIXED and GLIMMIX procedures in the SAS System V9, HLM6,¹⁷⁰ MLWin¹⁵⁹, Mplus¹⁷⁴ tailored for these analyses.

Two-level model for cross-sectional data analysis The statistical model for a “cross-sectional” analysis with one observation per client, for example Y =satisfaction at 6 months follow-up, is presented via two regression equations:

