We conducted sensitivity analyses for alternative representations of time as a continuous or class variable and for alternative weighting approaches. To investigate possible nonignorable effects, we used 2 methods. For continuous measures (such as MCS-12 and number of service visits), we multiplied ignorable-model imputations alternatively by 1.1 and 0.9 to reveal sensitivity to 10% departures from ignorable-model predictions with dichotomized versions of continuous measures (MCS-12 \leq 40) based on the imputed continuous value. For categorical imputations where reference cells were based on an underlying continuous measure (that is, predicted response propensity) including an indicator for any utilization and adjusted Bayesian bootstrap imputations reflecting unit nonresponse at a particular time point, nonignorable imputations for cases in nonboundary reference cells were generated by borrowing values from the reference cell with either the next higher or next lower value of the underlying continuous measure.¹⁹ We also conducted 12-month endpoint analysis controlling baseline with weighting adjustment and presented standardized predictions.^{2, 14}

Analyses for 3-year outcome:

We conducted 3 years endpoint analysis controlling baseline with weighting adjustment (see analysis strategy for 6 months). Given multiple secondary outcomes,¹⁹ we built on the false-discovery-rate (FDR) framework²⁰ as extended by Yekutieli and Benjamini²¹ and used both standard and FDR-adjusted p values (pFDR) in interpreting results across a large number of regression analyses. Results with pFDR $<$.05 are viewed as convincing evidence of a difference, and higher pFDR thresholds are considered as suggestive evidence. We separately calculated pFDR for the two primary outcomes, the community-prioritized outcomes, service use in the health care sector, service use in the social-community sector, medication use, and summary utilization indicators.

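### The rule for judging the two primary outcomes changes between waves, and the single-step Bonferroni rule used at 6 months gives up power that Holm would keep

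*Combined protocol and SAP*

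**What the plan says.** Four places bear on how the two primaries are judged.

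- **Section 5, Multiple Comparisons.** The results favouring one arm are to be counted and their share compared with one half. Two formal methods are then raised: "We will consider but will not rely solely on Bonferroni adjustments and related methods", and "We will also consider the false discovery rate (FDR". No method, family or level is fixed.
- **Section 5, Overview of the Aim 2 analyses.** "We will use two-sided tests with $p < .05$ for statistical significance". Whether the p-value is raw or adjusted is not said.
- **Appendix A4, 6-month outcome.** "We applied a Bonferroni adjustment considering two primary outcomes", namely MCS-12 of 40 or less and PHQ-9 of 10 or more. The per-test level is not printed; .025 each follows if the overall level is .05. On intervals: "Results of logistic regression models are presented as odds ratios (OR) and Poisson models as rate ratios (RR) with 95 % confidence intervals". There is no separate interval for the primaries.
- **Appendix A4, 3-year outcome.** "We separately calculated pFDR for the two primary outcomes, the community-prioritized outcomes", and for several service-use families. An FDR-adjusted p below .05 counts as convincing and higher values as suggestive; standard p-values are used as well.

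The 12-month part of Appendix A4 states no multiplicity rule.

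**The concern.** A primary outcome should meet one pre-stated standard. Here the standard depends on the section and the wave, and no reason is given for the change. Three things are at stake. A result with p between .025 and .05 may count or not according to which text is followed. A primary can fail the 6-month Bonferroni test while its printed 95% interval excludes 1. And the rule at the main time point is weaker than another rule with the same error guarantee, in a trial whose sample size was set at .05 per outcome.

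**Working it through.** **1. The level behind the design figures.** Inputs from Section 5 and Tables 4 and 5: 780 analysed (390 per arm), 80% power, two-sided .05, ICC 0 to .02, 80-100 programs, VIF = 1+(m-1)×ICC.

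- ICC 0: d ≈ (1.960+0.842)×√(2/390) = 2.80×0.0716 = 0.201.
- ICC .02, 80 programs: m = 780/80 = 9.75, VIF = 1+8.75×.02 = 1.175. With 78 degrees of freedom, d = 0.220 (0.216 with 100 programs).

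Table 4 prints 0.20-0.22, so it reproduces at .05 per outcome, not .025.

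**2. Verdicts for given p-value pairs (two tests, threshold .05 on the adjusted p).** Bonferroni doubles each p. Holm doubles the smaller p and sets the larger adjusted value to the greater of that and the larger raw p. Basic step-up FDR leaves the larger p as it is and gives the smaller the lesser of twice itself and the larger p. The dependency version multiplies the step-up values by 1+1/2 = 1.5.

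| p-values | Bonferroni | Holm | Step-up FDR | Dependency FDR |
|---|---|---|---|---|
| .03, .04 | .06, .08: none | .06, .06: none | .04, .04: both | .06, .06: none |
| .02, .20 | .04, .40: one | .04, .20: one | .04, .20: one | .06, .30: none |
| .01, .04 | .02, .08: one | .02, .04: both | .02, .04: both | .03, .06: one |

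Under either closed-form FDR reading, some pair is judged differently at 6 months and at 3 years.

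**3. Which FDR variant?** The 3-year text cites item 20 for the framework and item 21 for its extension. In the appendix list, item 20 is the paper on FDR under dependency, item 21 the classic FDR paper and item 22 a resampling version. Moving the numbers up by one would fit the wording and point to the resampling version, whose adjusted values cannot be worked out from two p-values alone. The documents do not settle it.

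**4. Intervals.** With p between .025 and .05, twice p exceeds .05, so Bonferroni fails, but the 95% interval excludes 1.

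**5. Power.** Assume that each outcome has 80% power at .05 (mean test statistic 2.80). At .025 the power is Φ(2.80-2.24) = 71.2%. At zero correlation, with .800-.712 = .088 falling between the two levels:

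- Bonferroni, both: .712² = 51%.
- Holm, per outcome: .712+.088×.712 = 77%.
- Holm, both: .80²-.088² = 63%.
- At least one, either rule: 1-.288² = 92%.

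The other rows come from 4,000,000 simulated bivariate normal pairs. The documents give no correlation, so the range is an assumption.

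| Correlation | Per outcome: Bonferroni / Holm | Both: Bonferroni / Holm | At least one: either |
|---|---|---|---|
| 0 | 71% / 77% | 51% / 63% | 92% |
| .3 | 71% / 77% | 54% / 66% | 88% |
| .5 | 71% / 76% | 57% / 68% | 85% |
| .7 | 71% / 76% | 60% / 70% | 82% |

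With both effects null, the chance of any false rejection is 4.3-4.9% under Bonferroni and the same under Holm. Bonferroni and step-up FDR disagree on at least one primary in 11-13% of trials at the design effect.

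**The case against.** The best defence is that Section 5 announced a flexible approach and the appendix carried it out: Bonferroni and the comparison with one half at 6 months, FDR at 3 years. Bonferroni is valid, and preferring Holm is a matter of efficiency. The 3-year study is a separately funded extension with its own aims, so the two rules never meet the same p-value. The depression outcome also differs slightly: PHQ-9 at 6 months, PHQ-8 at 3 years. Significance at 6 months rests on regression coefficients, so the interval is not the decision rule.

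Much of this is fair, and it rules out some stronger readings that a reader might infer.

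- *Section 5 tests the primaries with no adjustment.* The Overview read alone suggests this, and it would put family-wise error at about 8-10%. But the Multiple Comparisons paragraph keeps Bonferroni and FDR in play, and p<.05 could mean an adjusted p. The fault is that the choice is left open.
- *Two p-values of .04 fail at 6 months but are certainly convincing at 3 years.* That needs the basic step-up rule, which the text does not name. Under the dependency version both become .06.
- *The 3-year rule is lax.* With two tests the basic step-up rule is Hochberg's procedure, which still controls family-wise error under independence or positive dependence. The dependency version is stricter than Bonferroni in the .02/.20 case. The 3-year scale is also graded and uses raw p-values, so a flat reversal of verdicts overstates it.

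What the defence does not supply is a reason for changing the rule between waves, a rule for 12 months, or a label on the intervals.

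**Conclusion.** The point holds as an inconsistency in the error-control rule and an avoidable loss of power, not as a failure to control error. The rule for the primaries is open in Section 5, single-step Bonferroni at 6 months, absent at 12 months, and an unidentified FDR variant at 3 years. Holm has the same family-wise guarantee as Bonferroni, needs no extra assumption and never rejects less. Its gain is about 5-6 percentage points per outcome and 10-13 points for showing both, with none for showing at least one.

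These figures assume an overall level of .05, both true effects at the Table 4 size, and a correlation of 0 to .7. If only one effect is real, the gain is negligible: at correlation .3, power for the real effect is 71.3% under Bonferroni and 71.5% under Holm.

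**What to change.** - In Appendix A4, for 6 months, 12 months and 3 years, name one procedure for the two primaries: Holm at overall two-sided .05. Name Holm alone. Hochberg would reject both at .03 and .04 where Holm rejects neither, so the two cannot be offered as interchangeable.
- In the Section 5 Overview, say that p<.05 means the Holm-adjusted p-value for the primaries, and bring the Multiple Comparisons paragraph into line.
- Keep FDR for the secondary families, state the variant and correct its citation.
- Label the 95% intervals for the primaries as unadjusted for multiplicity. Switching to 97.5% intervals would not match Holm either: with p-values of .01 and .04 Holm rejects both, but the second 97.5% interval includes 1.

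The cost is wording and a few adjusted p-values; no new data are needed. There are two downsides. The intervals will not map one-to-one to the Holm decision. And Appendix A4 describes analyses in the past tense, so where they are complete the Holm result should stand beside the reported one (Bonferroni at 6 months, FDR at 3 years), labelled as a later change.
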